#### 4.8 Analyses of Exploratory Efficacy Variables

Exploratory efficacy variables will be analyzed the same way as the primary and secondary efficacy variables.

#### 5. SAFETY ANALYSES

Safety and tolerability will be evaluated based on the incidence of TEAEs, incidence of elicited reports of suicidal ideation or statements, self-injurious behaviors, and suicidality, incidence of AEs leading to termination and changes in vital signs, modified BMI z-score, ECG findings and laboratory measurements, and incidence of pre-specified abnormal laboratory test results. All safety data will be presented using the safety population.

#### 5.1 Treatment Emergent Adverse Events (TEAEs) and Potential Suicidality

Adverse events will be monitored continuously from the time a participant signs the informed consent document until the end of double-blind randomized treatment period (week 24). Similarly, reports of suicidal ideation or statements, self-injurious behaviors, and suicidality elicited from participants who are able to speak and understand the concepts and from all caregivers will be elicited at every contact and followed continuously during the double-blind treatment.

Medical and behavioral conditions that are present at screening and/or baseline will only be considered treatment emergent adverse events if their intensity increases significantly (i.e. numeric rating of intensity is increased) after screening and/or baseline.

TEAEs will be coded using the Systematic Longitudinal Adverse Event Scale (SLAES) mapping to MedDRA terms and MedDRA terms for TEAEs not mapped in the SLAES. Additional details about this scale are given in the protocol.

Intensity of adverse events will be categorized as mild, moderate, severe, life-threatening, or resulting in death. Relationship to treatment will be categorized as unknown or not applicable relationship, unrelated, possibly related, likely related, or certainly related. For FDA reporting, all possibly related, likely related and certainly related TEAEs will be considered related.

Overall summary of TEAEs, such as all TEAEs, TEAEs by intensity and TEAEs by relationship to treatment, will be summarized by category and preferred term for each treatment group and over all participants. TEAEs leading to participant withdrawal from the study, and TEAEs resulting in death will be listed separately.

Serious adverse events (SAE), defined using generally accepted criteria as stated in the protocol, will be listed and summarized by treatment group and participant experiencing at least one SAE. Relationship to treatment and outcome will be included in each listing.

All reports of suicidal ideation or statements, self-injurious behaviors, and suicidality will be listed by participant and treatment group.

No formal hypothesis-testing analysis of TEAEs or suicidality incidence rates will be performed.

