- 10. Added that the full analysis set will only include participants who have both a baseline and post-baseline ABC-SW, rather than just a post-baseline assessment of the primary outcome. (This reflects deletion of SF as a primary outcome measure.)
- 11. Specified that the demographics and baseline symptom measures will reflect only the full analysis set.
- 12. Clarified that age will reflect age at time of baseline visit rather than screening since there was often a lag of several months between screening and baseline for the early participants in the trial due to issues with study drug.
- 13. Deleted reporting of psychiatric history.
- 14. Will no longer adjust for multiplicity
- 15. Eliminated the following exploratory efficacy measures: Calibrated ADOS severity score, PDD-BI subscales replacing with PPD-BI screening version.
- 16. Eliminated Vineland 2 two domain composite score and maladaptive behaviors subscales, as well as measures listed in item 3.( above) from exploratory efficacy variables.
- 17. In Section 4.2, eliminated age group as a stratification variable, eliminated evaluation of two kinds of models instead using a mixed model with repeated measures (MMRM)
- 18. Specified thresholds for conducting sensitivity analyses for missing data.
- 19. Provided more detail related to SAS programming for primary analyses.
- 20. In Section 4.6 of SAP deleted examination of *OXTR* gene methylation and instead added examination of baseline serum oxytocin level.
- 21. Section 4.7 of SAP, removed bonferroni correction using simple two sample t-test instead
- 22. Error in section 4.8 of final SAP. Exploratory efficacy variables were analyzed in the same way as the key secondary efficacy analyses.
- 23. Section 5.1 changed severity of TEAEs to intensity paralleling changes in the SLAES.
- 24. Section 6, eliminated use of two primary outcomes.

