SOARS-B Parent Dose Sheet 		İχ	X	X	Х		Х	X	Х	X	X	X	
Risks Handout		İΧ				1			Х				
Medication Compliance 				Х	X	1	X	X	Х	X	X	X	X
Oxytocin Dosing Log (staff)	i	İx	İх	X	X		X	X	X	ΪX	X	l x	l x
Medication Diary Dispensed	1	X		X	X		X	X	X	X	X	X	

0-CGI-S only at baseline, CGI-I and CGI-S at most other time points (office visits)

- 1-Required at screening but can be done at any time during the course of the study at physician discretion. Must have a negative pregnancy test within two weeks of baseline
- 2-Safety labs to include: glucose (random), CO2, Cl, K, Na, Creatinine, BUN, AST, ALT, full urinalysis, urine pregnancy in pubertal girls Screening safety labs must be repeated if more than 12 months between screening and baseline
- 3- Assessment will be obtained only in participants who have fluent phrase speech & can define basic feelings and friendship
- 4- Completed each time the participant returns study medication
- 5- The appropriate SOARS-B Parent Dose Sheet should be given at each time dose changes to parents
  - 6-Stanford Binet or Mullen may be completed at physician discretion
  - 7- At physician discretion

  - \*Must be given at baseline, but also can be given at any other time during the course of the study at study staff discretion
    \*\*Optional redraw of mRNA, plasma/salivary oxytocin, and methylation at baseline for those who may have had a lengthy time between screening and baseline (not safety

Procedures for visits are allowed to be completed on separate days, however, subjects may not be dispensed open label medication until all week 24 procedures are completed

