## Trained Rater/Physician

Systematic Longitudinal Adverse Events Scale (SLAES): systematic elicitation and screening of adverse events will be completed using the SLAES. This will also be used at screening and baseline to obtain a comprehensive psychiatric and medical history of the patient.

Suicidality Assessment: The physician will use clinical judgment to determine if the participant understands the concepts of death and making one's self die or hurt. If the participant is deemed able to understand these concepts they will be asked if they have had any thoughts about wanting to die, wanting to hurt themselves, wanting to kill themselves and if s/he has done anything to hurt himself/herself so he/she would die or have done anything to hurt himself/herself for any other reason. If the participant is deemed not to understand these concepts, his/her caregiver will be queried by asking whether the child has said or done anything that makes the parent think the child wanted to die, to hurt himself/herself or to kill himself/herself and asking about suicidal behaviors. If any are endorsed, the caregiver will also be asked if this is a significant change in severity or frequency from the participant's baseline. The clinician will determine whether the behaviors clearly do not appear stereotypic, might be stereotypic and are clearly stereotypic (e.g. chronic repeated head banging or self biting).

Female Reproductive Form: We will record the last menstrual period, document irregular periods and verify continued use of two forms of birth control (if sexually active).

*Vital Signs:* Vital signs will be measured at each visit and will include heart rate, sitting blood pressure, and temperature.

Stanford Binet (5th edition): The Stanford-Binet intelligence scale is a standardized test that assesses intelligence and cognitive abilities in children and adults aged two to 85+ years. The Stanford-Binet Scale tests intelligence across four areas: verbal reasoning, quantitative reasoning, abstract/visual reasoning, and short-term memory. The areas are covered by 15 subtests, including vocabulary, comprehension, verbal absurdities, pattern analysis, matrices, paper folding and cutting, copying, quantitative, number series, equation building, memory for sentences, memory for digits, memory for objects, and bead memory. The abbreviated IQ (ABIQ) will be used for this study and includes non-verbal fluid reasoning and verbal knowledge subtests.

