## **8.1.1** Treatment Emergent Adverse Events

In this trial we are documenting all AE's, but analysis will focus only on Treatment Emergent AE's (TEAE's). Medical and behavioral conditions that are present at screening and/or baseline will only be considered treatment emergent adverse events if their severity increases significantly after the participant has taken at least one dose of study treatment. Intermittent conditions such as seasonal allergies will only be considered TEAEs, if the severity or frequency is significantly greater than in the previous two years. Only TEAEs will be considered in the adverse event safety analyses.

If a TEAE occurs, its relationship to study product (assessed only by those with the training and authority to make a diagnosis, which would include MD, DDS, DMD, PA, Nurse, Nurse Practitioner or DO), and resolution/stabilization will be coded at the resolution of the event or end of the subject's participation in the study. All TEAEs occurring while on study must be documented appropriately regardless of relationship. All TEAEs will be followed to adequate resolution. If a TEAE is a severe adverse event rating (3) and an Unexpected Problem (UP-no prior history of issue/not commonly seen in autistic patients and not described as a risk of the treatment), the UP form must be completed. If a TEAE is an SAE the the SAE form and SLAES (unscheduled visit) must be completed.

**Severity of Event:** All AEs will be assessed by the clinician using a protocol defined grading system. For events not included in the protocol defined grading system, the following guidelines will be used to quantify intensity.

- **Mild:** events require minimal or no treatment and do not interfere with the subject's daily activities.
- **Moderate:** events result in a low level of inconvenience or concern with the therapeutic measures. Moderate events may cause some interference with functioning.
- **Severe:** events interrupt a subject's usual daily activity and may require systemic drug therapy or other treatment. Severe events are usually incapacitating.
- Life-threatening: Substantial risk dying or requires intervention to prevent death
- Death related to AE: Subject died as a result of the event, self-explanatory

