#### •

#### **Schedule of Events:**

- Changed from months to weeks for greater precision of time points
- Eliminated in-person visits at Weeks 2 and 26
- Eliminated in-person visits at Weeks 32, 40, and 44
- Eliminated Month18/Week 72 follow-up due to lack of funding and time, replaced with AE follow-up approximately 4 weeks after treatment is stopped
- Added ABC-SW and PPD-BI SV to each in-person visit
- Switched collection of genetic measures and biological samples in open-label treatment from w32 to w36 to provide additional information about time course of biological measures
- Allowed for up to 18 months between screening and baseline with specification of measures that needed to be repeated due to unanticipated delay in access to study drug once screening was opened (~ summer 2013)
- Minimized the number of visits during open label treatment to weeks 28, 36, 48

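### SAP 5.1 drops the protocol's after-first-dose criterion for TEAEs, so worsening before any study drug may be counted as treatment-emergent

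*Combined protocol and SAP*

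**What the plan says.** SAP v2.0, section 5.1, gives one rule for conditions present at screening and/or baseline. They count as TEAEs only "if their intensity increases significantly (i.e. numeric rating of intensity is increased) after screening and/or baseline". The rule does not mention the first dose and does not say which of the two ratings is the reference. The same section starts collection before dosing: "Adverse events will be monitored continuously from the time a participant signs the informed consent document".

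Protocol v6.0, section 8.1.1, is the other current rule. A pre-existing condition is treatment-emergent only "if their severity increases significantly after the participant has taken at least one dose of study treatment". The TEAE section of SAP v1.0 had the same first-dose criterion.

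The summary of SAP changes has one entry on this section: "Section 5.1 changed severity of TEAEs to intensity paralleling changes in the SLAES". It does not mention the first dose.

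On the interval before dosing, the same summary says that "there was often a lag of several months between screening and baseline for the early participants in the trial", and the high-level summary of protocol changes records "Allowed for up to 18 months between screening and baseline".

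**The concern.** The two current documents define a TEAE differently, and the SAP governs the tables. An analyst who follows 5.1 literally, with screening as the reference, would count a rating that rose between screening and the baseline visit although the child had taken no study drug. The safety population does not prevent this, because it restricts which children are included and not when their events occurred.

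TEAE incidence is a named safety objective (SAP 1.2.2), is compared between arms in protocol Analysis 2a, and goes to the DSMB by arm (SAP 5.6). Section 5.1 plans no formal test, so readers will judge safety from the tables. In a trial of children aged 3 to 17, events unrelated to treatment that are added to both arms would make a real excess on oxytocin harder to see.

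**Working it through.** The documents give no TEAE rate, no TEAE power and no expected number of pre-dose worsenings, so there is no planned figure to reproduce. The check is a comparison of texts, followed by an illustration of scale.

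**1. What each reading does.** Three hypothetical children with SLAES intensity ratings at screening, at baseline (pre-dose) and on treatment:

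| Ratings | SAP 5.1, screening as reference | SAP 5.1, baseline as reference | Protocol 8.1.1 |
|---|---|---|---|
| 1, 2, 2 | TEAE | not a TEAE | not a TEAE |
| 2, 1, 2 | not a TEAE | TEAE | TEAE |
| 1, 1, 2 | TEAE | TEAE | TEAE |

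The protocol column takes the level at dosing as the starting point, which is the natural reading of its text. With the baseline rating as reference, the SAP agrees with the protocol in all three rows. With screening as reference it disagrees in two, in opposite directions: it counts worsening that came before any drug, and it misses a condition that eased by baseline and returned on treatment.

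**2. Does a baseline rating exist?** Yes. Protocol 7.1 says of the SLAES: "This will also be used at screening and baseline to obtain a comprehensive psychiatric and medical history of the patient". Protocol 6.2 places the first dose on the afternoon of the baseline visit, so that rating is effectively the last one before dosing.

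**3. Scale if pre-dose worsenings are counted.** Let p be the true on-treatment risk in an arm and q the probability of a counted pre-dose worsening. By randomization q is equal in the two arms in expectation; it is also taken as independent of the on-treatment event. Then

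- observed risk = 1 − (1 − p)(1 − q)
- observed risk difference = (p₁ − p₀)(1 − q)

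Inputs: agitation in the pilot study that used the same adverse-event instrument (protocol v6.0, section 1.3, Table 1), 2/12 = 16.7% on oxytocin and 1/13 = 7.7% on placebo. These are 8-week rates from 25 children and serve only as an example. The values of q are assumed.

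For q = 10%: oxytocin 1 − 0.8333 × 0.90 = 25.0%; placebo 1 − 0.9231 × 0.90 = 16.9%; difference 8.1 points; ratio 1.48.

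| q | Oxytocin v placebo | Risk difference (points) | Risk ratio |
|---|---|---|---|
| 0 | 16.7% v 7.7% | 9.0 | 2.17 |
| 2% | 18.3% v 9.5% | 8.8 | 1.92 |
| 5% | 20.8% v 12.3% | 8.5 | 1.69 |
| 10% | 25.0% v 16.9% | 8.1 | 1.48 |
| 20% | 33.3% v 26.2% | 7.2 | 1.27 |

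Initial insomnia in the same pilot (3/12 = 25.0% v 2/13 = 15.4%) behaves alike: from q = 0 to 20% the difference falls from 9.6 to 7.7 points and the ratio from 1.62 to 1.24. The difference shrinks only by the factor 1 − q; the ratio is more sensitive.

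**The case against.** The strongest reply is that 5.1 names baseline as well as screening. The SLAES is repeated at baseline and dosing starts that afternoon, so a sensible analyst would use the baseline rating and reach nearly the protocol's result. This is correct, and it means q may be close to zero. It does not settle the matter, because the and/or wording permits either reference and nothing else in 5.1 excludes events before dosing.

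Second, the rule is a restriction: a rise in rating is necessary for a TEAE, not stated to be sufficient, and the protocol's criterion is still in force. That is fair as logic. In practice 5.1 offers no other timing rule, so its sentence would serve as the definition.

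Third, a reader might infer that the SAP simply counts from screening, that pre-treatment events therefore do enter the comparison, and that the dilution is large. For example, assume a constant hazard with 20% placebo incidence over 24 weeks and a hazard ratio of 1.5. The risk ratio would be 1.42 with no gap, 1.18 with a 26-week gap and 1.07 with a 78-week gap. The arithmetic is right, but the documents do not support the inference:

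- The incidence and hazard ratio are assumptions with no source in the plan.
- One gap is applied to every child, whereas the reported lag is several months and concerns early participants. Eighteen months is a permitted maximum.
- The Schedule of Events footnote, "Screening safety labs must be repeated if more than 12 months between screening and baseline", is a contingency for laboratory tests and says nothing about typical gaps.
- The model counts every event, whereas the quoted rule covers only conditions present at screening or baseline.

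**Conclusion.** Wrong as written: SAP 5.1 contradicts protocol 8.1.1, leaves the reference rating unspecified, and the summary of SAP changes does not record the change. Two analysts could follow 5.1 literally and produce different TEAE tables, one of them inconsistent with the protocol.

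The effect on results is possible, not established. Worsening before dosing **may** be counted. If it is, the expected effect is equal in both arms and moves the contrast toward the null. Its size cannot be found from the documents: it is near zero under the baseline reading, and under the screening reading it depends on an unknown q. The illustrated range rests on q between 2% and 20% and on small pilot rates. The screening reading can also err the other way for an individual child, by missing an on-treatment return to an old screening level, so dilution by extra counts is not the only possible error.

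**What to change.** Reconcile SAP 5.1 with protocol 8.1.1. Define a TEAE as an event first reported after the first dose, or a SLAES intensity rating that rises above the last pre-dose (baseline) rating after the first dose. The SAP's clarification that a significant increase means a higher numeric rating can stay. List events reported between consent and first dose separately, and add the change to the summary of SAP changes.

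The last pre-dose rating is a better reference than the highest pre-dose rating. The protocol contains no highest-rating rule, and such a rule would hide a condition that was severe at a distant screening visit, mild at baseline and severe again on treatment.

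The cost is a few sentences of text. The SLAES ratings and the dosing log are already collected. Comparing visit ratings also avoids relying on onset dates, which protocol v6.0, section 8.1, does not list among the items collected for every event.

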#### 5.2 Vital Signs

Vital sign measurements will be summarized at each time point for the absolute value and for changes from baseline by treatment group. Alarm values will be determined prior to unblinding and the percent of participants with values in the alarm range will be summarized at each time point by treatment group.

All vital signs data will be available upon request.

#### 5.3 Weight and Body Mass Index

Weight and Height are measured at every study visit. These values will be used to determine the BMI and modified BMI z score at each time point. Changes in modified BMI z-score from baseline to Week 24 by treatment group will be summarized. All BMI data will be available upon request.

#### **5.4 Clinical Laboratory Evaluations**

Blood and urine samples for safety laboratory assessments will be collected at screening, and week 24. To the extent possible, blood samples will be obtained at approximately the same time of day and under non-fasting conditions. All safety labs will be processed by LabCorp.

Laboratory test results, including prolactin results, will be summarized by treatment at baseline and for changes from baseline. We will also summarize the percent of participants in each treatment group with values within alarm ranges, which will be defined prior to breaking the blind. The mean value and SD of the labs within alarm ranges will be summarized at each time point. All measurements within alarm ranges for each affected participant will be listed.

#### 5.5 12-lead Electrocardiogram (ECG)

A 12-lead ECG will be performed at screening, and week 24.

Interval data will be summarized at baseline and week 24 for the absolute value and for changes from baseline by treatment group. Intervals that are within alarm ranges will be summarized and listed by participant. Overall assessment of ECG as normal or abnormal will also be summarized by treatment group using counts and percentages.

#### 5.6 Safety Data Reported to the DSMB

Safety data will be submitted to the independent DSMB twice per year. The following summaries will be provided for review at each meeting, separated by treatment group:

- Summary table of participant disposition including number screened, number randomized, number completed, percent early terminated, and reasons for early termination.
- Listing of all participants terminating the study early with duration of treatment and reason for study discontinuation.
- Listing of all SAEs.
- Summary table of the number and percent of participants with TEAEs by severity.
- Summary table of the number and percent of participants with TEAEs by relationship to study drug.
- Summary table of the number and percent of participants with specific TEAEs leading to participant early withdrawal. .
- Summary table of the number and percent of participants with TEAEs by system organ class and preferred term by treatment group.
- Listing of all severe TEAEs.
- Summary table of the number and percent of participants with suicidal ideation or vocalizations, self-injurious behaviors and suicide attempts by treatment group.
- Listing of all suicidal ideation or vocalizations, self-injurious behaviors and suicide attempts by treatment group.
- Summary of the proportion of suicidal ideation or vocalizations, self-injurious behaviors and suicide
  attempts by treatment group that are judged to be more severe than the participant's baseline level
  of such behaviors.

Additional summaries of other study data, including efficacy data, may be provided if requested by the DSMB.

